### **ANNEX 3. ADDITIONAL INFORMATION**

#### **ST. GEORGE'S RESPIRATORY QUESTIONNAIRE (SGRQ)**

*This questionnaire is designed to help us learn much more about how your breathing is troubling you and how it affects your life. We are using it to find out which aspects of your illness cause you most problems, rather than what the doctors and nurses think your problems are.*

*Please read the instructions carefully and ask if you do not understand anything. Do not spend too long deciding about your answers.*

*Before completing the rest of the questionnaire:*

*Please tick in one box to show how you describe your current health:*

Very good	Good	Fair	Poor	Very poor
				

**UK/ English (original) version**

## St. George's Respiratory Questionnaire, Continued (Page 2 of 6)

### PART 1

#### Questions about how much chest trouble you have had over the past 4 weeks.

Please tick (✓) one box for each question:

	most days a week	several days a week	a few days a month	only with chest infections	not at all
1. Over the past 4 weeks, I have coughed:					
2. Over the past 4 weeks, I have brought up phlegm (sputum):					
3. Over the past 4 weeks, I have had shortness of breath:					
4. Over the past 4 weeks, I have had attacks of wheezing:					
5. During the past 4 weeks, how many severe or very unpleasant attacks of chest trouble have you had?					

Please tick (✓) one:

more than 3 attacks   
3 attacks   
2 attacks   
1 attack   
no attacks

6. How long did the worst attack of chest trouble last?  
(Go to question 7 if you had no severe attacks)

Please tick (✓) one:

a week or more   
3 or more days   
1 or 2 days   
less than a day

7. Over the past 4 weeks, in an average week, how many good days (with little chest trouble) have you had?

Please tick (✓) one:

No good days   
1 or 2 good days   
3 or 4 good days   
nearly every day is good   
every day is good

8. If you have a wheeze, is it worse in the morning?

Please tick (✓) one:

No   
Yes

## **St. George's Respiratory Questionnaire, Continued (Page 3 of 6)**

### **PART 2**

#### Section 1

How would you describe your chest condition?

**Please tick (✓) one:**

The most important problem I have

Causes me quite a lot of problems

Causes me a few problems

Causes no problem

If you have ever had paid employment.

**Please tick (✓) one:**

My chest trouble made me stop work altogether

My chest trouble interferes with my work or made me change my work

My chest trouble does not affect my work

#### Section 2

***Questions about what activities usually make you feel breathless these days.***

**Please tick (✓) in *each box* that applies to you these days:**

	True	False
Sitting or lying still		
Getting washed or dressed		
Walking around the home		
Walking outside on the level		
Walking up a flight of stairs		
Walking up hills		
Playing sports or games		

## St. George's Respiratory Questionnaire, Continued (Page 4 of 6)

### PART 2

#### Section 3

##### ***Some more questions about your cough and breathlessness these days.***

Please tick (✓) in **each box** that applies to you **these days**:

	True	False
My cough hurts		
My cough makes me tired		
I am breathless when I talk		
I am breathless when I bend over		
My cough or breathing disturbs my sleep		
I get exhausted easily		

#### Section 4

##### ***Questions about other effects that your chest trouble may have on you these days.***

Please tick (✓) in **each box** that applies to you **these days**:

	True	False
My cough or breathing is embarrassing in public		
My chest trouble is a nuisance to my family, friends or neighbours		
I get afraid or panic when I cannot get my breath		
I feel that I am not in control of my chest problem		
I do not expect my chest to get any better		
I have become frail or an invalid because of my chest		
Exercise is not safe for me		
Everything seems too much of an effort		

#### Section 5

##### ***Questions about your medication, if you are receiving no medication go straight to section 6.***

Please tick (✓) in **each box** that applies to you **these days**:

	True	False
My medication does not help me very much		
I get embarrassed using my medication in public		
I have unpleasant side effects from my medication		
My medication interferes with my life a lot		

## St. George's Respiratory Questionnaire, Continued (Page 5 of 6)

### PART 2

#### Section 6

***These are questions about how your activities might be affected by your breathing.***

Please tick (✓) in **each box** that applies to you ***because of your breathing:***

	True	False
I take a long time to get washed or dressed		
I cannot take a bath or shower, or I take a long time		
I walk slower than other people, or I stop for rests		
Jobs such as housework take a long time, or I have to stop for rests		
If I walk up one flight of stairs, I have to go slowly or stop		
If I hurry or walk fast, I have to stop or slow down		
My breathing makes it difficult to do things such as walk up hills, carrying things up stairs, light gardening such as weeding, dance, play bowls or play golf		
My breathing makes it difficult to do things such as carry heavy loads, dig the garden or shovel snow, jog or walk at 5 miles per hour, play tennis or swim		
My breathing makes it difficult to do things such as very heavy manual work, run, cycle, swim fast or play competitive sports		

#### Section 7

***We would like to know how your chest usually affects your daily life.***

Please tick (✓) in **each box** that applies to you ***because of your chest trouble:***

	True	False
I cannot play sports or games		
I cannot go out for entertainment or recreation		
I cannot go out of the house to do the shopping		
I cannot do housework		
I cannot move far from my bed or chair		

## **St. George's Respiratory Questionnaire, Continued (Page 6 of 6)**

Here is a list of other activities that your chest trouble may prevent you doing. (You do not have to tick these, they are just to remind you of ways in which your breathlessness may affect you):

- Going for walks or walking the dog
- Doing things at home or in the garden
- Sexual intercourse
- Going out to church, pub, club or place of entertainment
- Going out in bad weather or into smoky rooms
- Visiting family or friends or playing with children

Please write in any other important activities that your chest trouble may stop you doing:

.....  
.....  
.....

Now would you tick in the box (one only) which you think best describes how your chest affects you:

- It does not stop me doing anything I would like to do
- It stops me doing one or two things I would like to do
- It stops me doing most of the things I would like to do
- It stops me doing everything I would like to do

*Thank you for filling in this questionnaire. Before you finish would you please check to see that you have answered all the questions.*

## **Modified Medical Research Council (mMRC) Dyspnea Scale**

### **Grade**

- 0 "I only get breathless with strenuous exercise"
- 1 "I get short of breath when hurrying on the level or walking up a slight hill"
- 2 "I walk slower than people of the same age on the level because of breathlessness, or I have to stop for breath when walking on my own pace on the level"
- 3 "I stop for breath after walking about 100 yards or after a few minutes on the level"
- 4 "I am too breathless to leave the house" or "I am breathless when dressing"

[figure not shown]
NB: This is the modified MRC scale that uses the same descriptors as the original MRC scale in which the descriptors are numbered 1-5. The modified MRC scale (0-4) is used for calculation of BODE index.

## **Cough - Visual Analogue Scale (Cough - VAS)**

## Patient's Assessment of Cough VAS

How much cough have you had because of your idiopathic pulmonary fibrosis (IPF) in the past week?

Place a vertical (|) mark on the line to indicate the intensity of the cough.

**Simplified Medication Adherence Questionnaire (SMAQ)**

Adapted for the treatment of idiopathic pulmonary fibrosis (IPF)

1. Do you ever forget to take your medication for IPF?	YES NO
2. Do you always take your medication for IPF at the indicated time?	YES NO
3. Sometimes if you feel worse, do you stop taking your medication for IPF?	YES NO
4. Did you miss your medication for IPF last weekend?	YES NO
5. Think on the last week.  How often did you miss your medication for IPF?	A: Never B: 1 - 2 C: 3 - 5 D: 6 - 10 E: More than 10
6. Think on the past 3 months.  a) How many days have you missed your medication for IPF?  b) How many days have you missed one of the two daily doses of your medication for IPF?	Days _____  Days _____

Adapted from (1) Validation of a simplified medication adherence questionnaire in a large cohort of HIV-infected patients: the GEEMA Study. Knobel H, Alonso J, Casado JL, Collazos J, Gonzalez J, Ruiz I, Kindelan JM, Carmona A, Juega J, Ocampo A; on behalf of the GEEMA Study Group. AIDS 2002;16(4):605-13.

SMAK - United States/English / Mapi.  
SMAQ\_TS1.0\_eng-USori.doc

**Simplified Medication Adherence Questionnaire (SMAQ),  
Continued (Page 2 of 2)**

The patient is considered non-adherent if:

- 1: YES
- 2: NO
- 3: YES
- 4: YES
- 5: C, D or E
- 6: a) More than two (2) days
- b) More than four (4) days

The questionnaire is dichotomic, any answer in the sense of non-adherent is considered non-adherent.

You can use the question number 5 as semi-quantitative:

- A: 95 - 100% compliance
- B: 85-94%
- C: 65-84%
- D: 30-64%
- E: < 30%

Adapted from (1) Validation of a simplified medication adherence questionnaire in a large cohort of HIV-infected patients: the GEEMA Study. Knobel H, Alonso J, Casado JL, Collazos J, Gonzalez J, Ruiz I, Kindelan JM, Carmona A, Juega J, Ocampo A; on behalf of the GEEMA Study Group. AIDS 2002;16(4):605-13.

SMAK - United States/English / Mapi.  
SMAQ\_TS1.0\_eng-USori.doc

## GAD - 7

### GAD-7

Over the last 2 weeks , how often have you been bothered by the following problems? (Use "✓" to indicate your answer)	Not at all	Several days	More than half the days	Nearly every day
1. Feeling nervous, anxious or on edge	0	1	2	3
2. Not being able to stop or control worrying	0	1	2	3
3. Worrying too much about different things	0	1	2	3
4. Trouble relaxing	0	1	2	3
5. Being so restless that it is hard to sit still	0	1	2	3
6. Becoming easily annoyed or irritable	0	1	2	3
7. Feeling afraid as if something awful might happen	0	1	2	3

(For office coding: Total Score  $T$        =       +       +      )

Developed by Drs. Robert L. Spitzer, Janet B.W. Williams, Kurt Kroenke and colleagues, with an educational grant from Pfizer Inc. No permission required to reproduce, translate, display or distribute.

## 2. LIST OF ABBREVIATIONS

Term	Definition / description
AE	Adverse Event
ATC	Anatomic Therapeutic Classification System
BAL	Bronchoalveolar Lavage
BSL	Baseline
CAD	Coronary Artery Disease
CTP	Clinical Trial Protocol
CTR	Clinical Trial Report
CV	Cardiovascular
DL CO	Diffusing Capacity for Carbon Monoxide
FAS	Full Analysis Set
FEV 1	Forced Expiratory Volume
FVC	Forced Vital Capacity
FU	Follow Up
GAD-7	Generalized Anxiety Disorder Screener Questionnaire
GAP	gender (G), age (A) and two lung physiology variables (P)
HRCT	High Resolution Computer Tomography
HRQoL	Health Related Quality of Life
ICF	Inform Consent Form
ICH	International Conference On Harmonisation
IPF	Idiopathic Pulmonary Fibrosis
LTOT	Long Term Oxygen Therapy
MedDRA	Medical Dictionary For Regulatory Activities
mMRC	modified Medical Research Council scale
MMRM	Mixed Models for Repeated Measures
PPS	Per Protocol Set
PT	Preferred Term
PD	Protocol Deviation
SD	Standard Deviation
SGRQ	St. George's Respiratory Questionnaire
sMAQ	Simplified Medication Adherence Questionnaire
SAE	Serious Adverse Event
SOC	System Organ Class
TLC	Total Lung Capacity
ToC	Table of Contents
TS	Treated Set
TSAP	Trial Statistical Analysis Plan
UIP	Usual Interstitial Pneumonia
VAS	Visual Analogue Scale

### **3. INTRODUCTION**

As per ICH E9 (1), the purpose of this document is to provide a more technical and detailed elaboration of the principal features of the analysis described in the protocol, and to include detailed procedures for executing the statistical analysis of the primary and secondary variables and other data.

This TSAP assumes familiarity with the Clinical Trial Protocol (CTP). In particular, the TSAP is based on the planned analysis specification as written in CTP Section 9.7 “Data Analysis”. Therefore, TSAP readers may consult the CTP for more background information on the study, e.g., on study objectives, study design and population, treatments, definition of measurements and variables, planning of sample size. SPSS Version 24 will be used for all analyses.

**4. CHANGES IN THE PLANNED ANALYSIS OF THE STUDY**

## **5. ENDPOINTS(S)**

### **5.1 PRIMARY ENDPOINT(S)**

The primary objective is to evaluate the HRQoL change from baseline of IPF patients treated with nintedanib in the current clinical practice in Greece, at the time-points of 3, 6, 9 and 12 months over a 52-weeks period via SGRQ instrument.

The following surrogate endpoints will be employed to assess the objective:

- The mean change from baseline of SGRQ total score until month 3, month 6, month 9 and month 12.
- The mean change from baseline of SGRQ symptoms domain score until month 3, month 6, month 9 and month 12.
- The mean change from baseline of SGRQ activity domain score until month 3, month 6, month 9 and month 12.
- The mean change from baseline of SGRQ psycho-social impact domain score until month 3, month 6, month 9 and month 12.

### **5.2 SECONDARY ENDPOINT(S)**

#### **5.2.1 Key secondary endpoint(s)**

Not Applicable

#### **5.2.2 Secondary endpoint(s)**

The following endpoints will be employed to assess the secondary study objectives:

- The mean change from baseline of mMRC questionnaire score until month 3, month 6, month 9 and month 12.
- Percentage of patients by dyspnoea severity according to mMRC questionnaire at month 3, month 6, month 9 and month 12.
- The mean change from baseline of Cough-VAS score until month 3, month 6, month 9 and month 12.
- Percentage of adhered / non- adhered patients to nintedanib treatment via SMAQ Questionnaire at month 3, month 6, month 9 and month 12.

- The mean change from baseline of GAD7 score until month 3, month 6, month 9 and month 12.
- Percentage of patients that used at least once LTOT at month 3, month 6, month 9 and month 12

## **6. GENERAL ANALYSIS DEFINITIONS**

### **6.1 TREATMENT(S)**

Patients enrolled in the current trial are recently diagnosed IPF patients and they have already initiated treatment with Nintedanib according to their physician's clinical decision.

No treatment intervention is relevant and therefore no special treatment assignment is under consideration.

### **6.2 IMPORTANT PROTOCOL DEVIATIONS**

Table 6.2:1 Important protocol deviations

Category/ Code	Description	Requirements	Excluded from
A	Entrance criteria not met		
A1.1	Inclusion criteria not met as specified in the protocol:	
The following inclusion criteria not met
 
 
• Patients <math>\geq 40</math> years of age.
 
• Treatment naïve patients with initial IPF diagnosis no more than 3 months prior to enrolment according to 2011 ATS/ERS/JRS/ALAT guidelines who are initiating treatment with Nintedanib (as monotherapy for IPF) or have initiated treatment with Nintedanib (as monotherapy for IPF) within the past 7 days prior to the enrolment.*
 
• Patients for whom the decision to prescribe therapy with Nintedanib according to the locally approved product's SmPC has already been taken prior to the study enrolment and is clearly separated from the physician's decision to include patient in the current study. *
 
• Patients that are able to read, understand and complete the study specific questionnaires. *
 
	PPS
A2	Exclusion criteria met		PPS
B	Informed consent		
B1	Informed consent not available/not done	Informed consent date missing	TS, PPS
B2	Informed consent too late	Informed consent date <actual consent date> was after Visit 2 date <Visit 2 date>	
D	Concomitant medication		
D2	Prohibited medication use	Pirfenidone taken.*	PPS
D3	Mandatory medication not taken	Nintedanib treatment was not taken or interrupted	PPS

Category/ Code	Description	Requirements	Excluded from
		for 28 days period*	
E	Certain Violations of procedures used to measure primary data		
E1	Protocol amendment / incorrect CRF, implemented after the approvals and/or PI signature	Incorrected (old) version of SGRQ questionnaire is completed after the IRB approvals*	PPS
F	Certain Violations of time schedule to measure primary data		
F1	No follow-up visits performed	Only baseline visit is recorded	PPS

Note: (\*) not programming activity checks. These IPV definitions in the TSAP should be made available to the Local Clinical Monitors (CMLs)/Clinical Research Associates (CRAs) to view so they know which IPVs are programmed and hence do not need to be identified at a site level on the manual PV log.”

### 6.3 SUBJECT SETS ANALYSED

The following sets will be used for the purpose of the statistical analysis of the current trial:

Treated Set (TS): all subjects entered the trial received at least once Nintedanib during the trial. TS will be used for safety analysis. Any analysis on primary, secondary and safety endpoints will be performed in TS.

Per Protocol Set (PPS): all subjects who have completed the trial with no major protocol deviations. PPS will be used only as supportive to the TS and only in the analysis of the primary endpoint providing that the TS does not differ more than 20% from the PPS in the number of patients.

Table 6.3:1 Subject Sets Analysed

Class of endpoint	Subject Sets	
	TS	PPS
Primary endpoints	primary analysis	secondary analysis
Secondary endpoints	X	
Safety endpoints	X	
Demographic/baseline endpoints	X	

## **6.5 POOLING OF CENTRES**

This section is not applicable because center/country will not be included in the statistical modeling.

## **6.6 HANDLING OF MISSING DATA AND OUTLIERS**

No imputation technique to fill in any missing values will be employed. Accordingly, the Last Observation Carried Forward technique or any other multiple imputation will not be applied.

Missing values will be differentiated from negative answers. Summary statistics will be performed only on subjects with available information (unknown data will not account in the total population for each specific variable).

For missing or incomplete AE dates or drug administration dates, or other significant dates, the BI internal procedures and guidelines (2) will be employed.

In case implausible data remain in the database once locked, then: for tables that are provided for endpoints with a large amount of implausible data, median, quartiles and percentiles should be preferred to mean, standard deviation, minimum and maximum.

Correction of implausible data on an individual subject case is not permitted.

In order to account for the missing values of the primary and secondary continuous endpoints, an MMRM model will be employed based on the assumption that values as missing at random.

Note: Due to incorrect translation in the Greek language of question 17 of the SGRQ instrument this specific question has been set to missing in all patients prior to the approval receipt date as mentioned in [Table 9.1:1](#). The corrected version to be considered is the one used after the approval receipt date. No further action is to be performed to impute this data for the primary analysis of the primary

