### 7.4 PRIMARY ENDPOINT(S)

#### 7.4.1 Primary analysis of the primary endpoint(s)

The SGRQ Total score and the corresponding sub domains will be calculated; it summarizes the impact of the disease on the overall health status. Scores are expressed as a percentage of

overall impairment where 100 represents worst possible health status and 0 indicates best possible health status.

The primary endpoint of SGRQ Total score and the corresponding sub domains will be summarized descriptively as continuous variables at each study visit in the TS population.

The SGRQ scores to be displayed in the above mentioned summaries will be the observed values at each visit and the absolute change from baseline at each visit.

Calculation of SGRQ score for each patient is performed on patient level based on the questionnaire manual.

Change from baseline is defined as post baseline – baseline value, assuming that both time points are non missing.

Baseline value: SGRQ following to ICF signature, see [Table 6.7:1](#).

Post baseline value: Any SGRQ score after the baseline visit.

For the statistical inference regarding the SGRQ Total score and the corresponding sub domains, mixed models for repeated measurements model (MMRM) assuming random missingness will be fit. The dependent variable will be the SGRQ (Total score or the corresponding subdomains) at each visit. Visit, GAPBSL stage, FVCBSL (cut off  $\leq 70\%$ ), DLCOBSL (cut off  $< 40\%$ ) and number of comorbidities (as dictated by the medical history page) will be entered as fixed factors, baseline score by visit as interaction term.

Patients will be fitted at random and an unstructured correlation matrix will be used, allowing adjustment for correlations between study visits within the study patients. The Kenward-Roger degrees of freedom approximation will be used in the model (ddfm=kr). In case of no convergence, the following steps will be considered:

- The value used in the model as tolerance in checking singularity should be changed to 10-10 (the default value is 10-12).
- Increase the number of convergence iterations to 200 (default is 100 iterations).
- Apply scoring algorithm. Request to use the Fisher scoring algorithm up to the 4th iteration. The default is 1.

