- Use a simpler covariance matrix: Should none of the previous methods does not work, the covariance matrix will be changed from unstructured to Toeplitz with heterogeneous variances. Should this also not converge, a standard Toeplitz matrix will be fitted. Finally, if convergence still does not occur, then an order-1 autoregressive matrix (AR(1)) can be fitted.

Summaries of the estimated mean change from baseline of SGRQ scores until months 3, 6, 9 and 12 will be provided with 95% confidence interval. Model information will be provided as footnote under the corresponding table.

Worth to note, that the response to incorrectly translated question 17 will be set to missing for any analysis mentioned above in all patients prior to the approval receipt date as mentioned in [Table 9.1:1](#).

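### On the likelier reading, SGRQ question 17 is blanked before the approval receipt date and scored after it, so patients with visits on both sides of that date get a primary change score built on two item sets (minor)

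*SAP*

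**What the plan says.** - **SAP 6.6, note.** Because of a wrong Greek translation, "this specific question has been set to missing in all patients prior to the approval receipt date". Then: "The corrected version to be considered is the one used after the approval receipt date". For the primary analysis the blanked item is not imputed; the note breaks off at that point. The same section has the general rule "Missing values will be differentiated from negative answers".
- **SAP 7.4.1.** The rule is repeated for the primary summaries and the model: "the response to incorrectly translated question 17 will be set to missing for any analysis mentioned above in all patients", with the same date limit. "Change from baseline is defined as post baseline" minus the baseline value, on the sole condition that both values exist. Scoring follows the questionnaire manual.
- **SAP 7.4.1, model.** "The dependent variable will be the SGRQ (Total score or the corresponding subdomains) at each visit". The other terms are visit, GAP stage, FVC, DLCO, number of comorbidities and baseline score by visit.
- **SAP 6.2, code E1.** This deviation is defined as "Incorrected (old) version of SGRQ questionnaire is completed after the IRB approvals", and it excludes from the per-protocol set only. SAP 6.3 adds: "PPS will be used only as supportive to the TS".

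Not visible are Table 9.1:1 (the approval date or dates), the end of the 6.6 note, a contents entry between 7.4.1 and 7.5, and the scoring manual.

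**The concern.** Changes in the SGRQ total and domain scores are the primary endpoint. A change score is meant to compare a patient with himself or herself on the same instrument. If question 17 is absent from the baseline score and present in a later one, part of the difference comes from the change of form and not from the patient. The legible text does not require the same items at both visits.

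Patients on both sides of the date are very likely. Data collection began on 28 February 2019 (Protocol 6), each patient is followed for 52 weeks, and the SAP of 1 April 2020 already speaks of the item as blanked.

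**Working it through.** **1. Which reading?** The phrase about all patients prior to the date has two readings.
- *By patient*: question 17 is blank at every visit for patients enrolled before the date. Each patient's change then uses one item set.
- *By response*: question 17 is blank only in assessments made before the date.

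Three passages favour the second reading. SAP 7.4.1 blanks the response to the wrongly translated item. SAP 6.6 names the form used after the date as the one that counts. Code E1 turns on when the old form was completed, although it does not itself say how earlier responses are scored. The first reading is not excluded.

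**2. What follows for a spanning patient.** Let w be the weight share of question 17, I its score and R the score on the other items (0-100). Under prorated scoring (assumed; the manual is not visible), the score without the item is R and the score with it is (1 - w)R + wI. The later visit therefore carries an extra w(I - R). None of the model terms listed in 7.4.1 codes the form version. Adjusting for baseline score by visit does not remove a shift that affects only spanning patients' later scores.

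**3. The plan's own precision.** Protocol Table 3 uses N = 200 and SD 16-22. The half-width is 1.96 x SD / sqrt(200).
- SD 16: 2.22. With mean 2 this gives -0.2 to 4.2, width 4.4, as printed.
- SD 22: 3.05, width 6.1, as printed.

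**4. Illustration of size.** Inputs from the protocol: 240 patients, 36 months of recruitment, visits at 3, 6, 9 and 12 months, 50 SGRQ items. Assumed: uniform accrual, one approval date at recruitment month A, w = 1/50 = 2%, and an average gap I - R of 10 to 50 points in one direction.

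Per spanning patient: 0.02 x 10 = 0.2 to 0.02 x 50 = 1.0 points.

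A patient enrolled at month t spans at visit v if t < A < t + v, so the share is min(v, A)/36. Mean shift = share x 0.2 to 1.0.

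| A (months) | Share at 3, 6, 9, 12 months | Patients at month 12, before dropout | Month-12 shift in total |
|---|---|---|---|
| 3 | 8, 8, 8, 8% | 20 | 0.02-0.08 |
| 6 | 8, 17, 17, 17% | 40 | 0.03-0.17 |
| 9 | 8, 17, 25, 25% | 60 | 0.05-0.25 |
| 12 or later | 8, 17, 25, 33% | 80 | 0.07-0.33 |

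Relative to the half-widths, the extremes are 0.017/3.05 = about 0.5% and 0.333/2.22 = 15%.

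The SAP date is 398 days, or 13.1 months, after the start of data collection. If Table 9.1:1 was complete by then (an inference), A is at most 13.1.

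**5. Variations.**
- *Dropout of 17-20% unrelated to spanning*: the share is unchanged, and the 80 patients become 240 x 0.80/3 = 64 to 240 x 0.83/3 = 66.
- *Slow start* (accrual rate rising linearly over 12 months, then flat; 6 + 24 = 30 units): A = 6 gives 1.5/30 = 5% and 0.01-0.05 points; A = 12 gives 6/30 = 20% and 0.04-0.20 points.
- *Affected domain*, if it has 16-26 equally weighted items (assumed): 10/26 = 0.38 to 50/16 = 3.13 points per spanning patient. The month-12 mean shift is 0.06-0.52 at A = 6 and 0.13-1.04 at A = 12 or later. The English sample in Protocol Annex 3 numbers only the first eight questions, so the documents do not settle which domain this is.

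**The case against.** The case against has four parts.

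- **The text is ambiguous.** If blanking by patient was meant, within-patient change is already consistent and only a clarification is needed. This stands as a possibility, so the point is put as the likelier reading and not as established.
- **It may be handled where we cannot see.** The 6.6 note limits its no-imputation statement to the primary analysis, and a contents entry after 7.4.1 is redacted. A reader might infer that no sensitivity analysis for question 17 is planned; the documents do not support that. Such an analysis would, however, leave the primary change score as defined in 7.4.1 unchanged.
- **The size is assumed throughout.** Weight, gap, prorating, accrual and date are all inputs. The 10-50 range leaves out gaps near zero, and the upper end needs a 50-point average gap in one direction. Gaps of mixed sign would partly cancel. This stands in full.
- **The study is descriptive.** Protocol 9.7.1 tests no hypothesis. The only reference difference given is 4 points, from COPD, and the largest illustrative shift in the total is about one twelfth of it (0.33/4). This limits the severity.

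A reader might also infer that old forms completed after approval keep their wrong answers in the primary analysis, because the rule is tied to a date and E1 excludes only from the per-protocol set. That is largely answered: 7.4.1 attaches the blanking to the incorrectly translated item, and 6.6 says the corrected version is the one that counts after the date.

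**Conclusion.** The point holds in a limited form. On the likelier, response-level reading, patients whose visits fall on both sides of the approval date have a primary change in SGRQ total, and in the domain holding question 17, that mixes two item sets. The model has no term that removes it.

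The number of patients and the size and sign of the artefact cannot be fixed from the documents. Under the stated assumptions, 8-33% of patients span at month 12 and the mean total shifts by about 0.02-0.33 points against half-widths of 2.2-3.05. A gap near zero or of mixed sign would give less; the affected domain would shift more.

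Two stronger conclusions are tempting and unsupported. One is that the primary result is materially biased: even the upper illustrative figure is small beside the planned precision. The other is that the artefact always runs towards apparent worsening, as it could if a blank were scored as zero. The 6.6 rule separating missing values from negative answers speaks against that, and the scoring manual is not visible.

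Severity is minor: a cheap gain in within-patient consistency.

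**What to change.** 1. For every patient with any assessment on the old form, score the SGRQ total and the affected domain without question 17 at all visits, so that each change uses one item set.
2. In SAP 6.6, define the blanking by form version and not by date, in line with the wording of 7.4.1. This also settles old forms used after approval.
3. Report the number of spanning patients at each visit.
4. If blanking by patient was already meant, say so in 6.6.

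The cost is SAP wording and one scoring change, with no new data. The downside is that patients with any old form lose one item at all visits, including valid corrected answers, so their score is not the exact published total. Visit means across patients would still mix item sets, as they do under the present rule; within-patient change would not.

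### SGRQ question 17 is set to missing by approval date, not by the form completed, so under the visible SAP text a mistranslated answer on an old form used after approval is scored in the primary analysis

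*SAP*

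**What the plan says.** The note that closes SAP 6.6 reports the translation error in question 17 and states that "this specific question has been set to missing in all patients prior to the approval receipt date", with the date given in Table 9.1:1. It then adds: "The corrected version to be considered is the one used after the approval receipt date". Section 7.4.1 repeats the rule for the primary analysis: the answer to "incorrectly translated question 17 will be set to missing for any analysis mentioned above in all patients prior to the approval receipt date".

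Table 6.2:1 in SAP 6.2 lists, as important deviation E1: "Incorrected (old) version of SGRQ questionnaire is completed after the IRB approvals". The only analysis set named in its exclusion column is the PPS. E1 carries an asterisk, which the table note explains as "not programming activity checks", so these cases are found by hand.

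On the analysis sets, SAP 6.3 says "Any analysis on primary, secondary and safety endpoints will be performed in TS" and "PPS will be used only as supportive to the TS". The PPS analysis is limited to the primary endpoint and is run only if the two sets differ by no more than 20% in patient numbers.

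**The concern.** What makes a question 17 answer unusable is the wording the patient read. The rule in 6.6 and 7.4.1 uses a calendar date in its place. The two agree only if every site switched forms on the date, and E1 exists because the SAP expects that some may not have. For those forms the SAP records the defect but does not carry it into the scoring of the set that matters most.

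At stake is the primary endpoint itself: the SGRQ total and whichever domain holds question 17. If the old form was used at a baseline visit that fell after approval, the wrong answer also reaches every change score for that patient, because 7.4.1 subtracts the baseline score and uses it by visit in the model.

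**Working it through.** **Step 1. The rule, case by case.** I take the approvals named in E1 and the approval receipt date in 6.6 to be the same event. Table 9.1:1 would confirm this.

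| Form completed | Timing | Question 17 in the TS (primary) | Patient in the PPS |
|---|---|---|---|
| Old translation | Before the date | Set to missing (6.6, 7.4.1) | Not excluded on this ground |
| Corrected translation | After the date | Scored | Not excluded on this ground |
| Old translation | After the date (E1) | No visible rule sets it to missing, so scored | Excluded (Table 6.2:1) |

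The first and third rows have the same faulty item. They differ only in date, yet in the primary set one answer is removed and the other is used.

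**Step 2. Would the PPS analysis show the effect?** It is the only visible analysis that leaves out E1 patients. Inputs: 240 enrolled and 17-20% dropout (Protocol 9.5); PPS members must have completed the study and the 20% limit applies (SAP 6.3). Assume that all 240 are in the TS and that the 20% is taken relative to the TS.
- Smallest permitted PPS: 240 × (1 − 0.20) = 192.
- Completers at 17% dropout: 240 × 0.83 = 199.2. The margin is 7.2, so about eight further exclusions for any deviation cancel the analysis.
- Completers at 20% dropout: 240 × 0.80 = 192. The margin is zero, so one further exclusion cancels it.

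The PPS comparison may therefore not be run.

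**Step 3. Size.** The plan gives no figure on this point. As a yardstick I reproduced the precision in Protocol Table 3 for 200 evaluable patients, with half-width 1.96 × SD/√200:
- SD 16: 2.22, full width 4.43 (Table 3: 4.4).
- SD 22: 3.05, full width 6.10 (Table 3: 6.1).

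The shift in a visit mean is w × f × s, where w is the weight of question 17 in points of the total, f the share of that visit's forms that are old ones used after approval, and s the mean error in the item as a fraction of its scale. None of the three is in the documents. All are assumptions: w 1 to 4, f 5% to 30%, s 25% to 100%.
- Low: 1 × 0.05 × 0.25 = 0.0125 points.
- Middle: 2 × 0.10 × 0.50 = 0.1 points, about 5% of the narrower half-width (0.1/2.22).
- High: 4 × 0.30 × 1.00 = 1.2 points, about 54% of the narrower half-width (1.2/2.22) and 39% of the wider one (1.2/3.05).

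The high value needs all three factors at their extreme and every error in the same direction. If there are no E1 forms, f is zero and so is the shift. One item would be a larger part of its domain score than of the total, but the domain cannot be identified: the questionnaire in Protocol Annex 3 numbers only its first eight items.

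**The case against.** The strongest reply is that the relevant text cannot all be seen. Table 9.1:1 is not in the public copy, the note in 6.6 breaks off mid-sentence, and the subsection after 7.4.1 is blacked out. Section 6.6 describes the blanking in the past tense, so it may have been done in data management, possibly form by form. The sentence about the corrected version can also be read as saying which version counts, rather than that every later form is that version. This stands as a limit on confidence. It does not remove the gap, because the operative wording in both 6.6 and 7.4.1 is a date, and a sensitivity analysis elsewhere would not change the primary rule.

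A second reply is that E1 may be precautionary and have no cases, in a study whose protocol (9.7.1) calls its analyses exploratory and descriptive. That also stands, and it limits the importance of the point.

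Three stronger readings are tempting, and the documents support none of them.
- A reader might infer that the primary results are materially biased, or that wrong answers cluster in the visits just after approval. No document gives the number or timing of old forms, the item weight or the direction of error.
- A reader might infer that excluding E1 patients from the PPS is itself wrong, since the same old form before approval costs nobody their place. But before approval the old form was the one in use, and afterwards using it is a conduct deviation. Excluding important deviations is what a per-protocol set does.
- A reader might put a figure on the patients lost to the PPS through E1. The share of E1 patients is unknown, and the PPS analysis may not be run.

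**Conclusion.** The gap is real and narrow. Under the visible text, question 17 on an old-translation SGRQ completed after the approval receipt date is scored as valid in the primary TS analysis, although the SAP treats the same answer as unusable before that date and expects such forms to occur. This is a stated rule that gives the wrong score for a foreseen case, not just missing detail.

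The effect is unknown in size and probably small for the total score. The 0.01 to 1.2 point range rests wholly on assumed weight, share and error, and the true number of affected forms may be zero. Confidence is medium, because the table of dates and the text after 7.4.1 could not be checked.

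**What to change.** In SAP 6.6 and 7.4.1, replace the date condition with a form-version condition: question 17 is set to missing on every SGRQ completed on the old translation, whatever its date, with such forms identified from the E1 log and the stored questionnaires. Report the number of these forms by visit. The E1 exclusion from the PPS can stay. Scoring then follows the questionnaire manual, as it already does for old forms completed before approval.

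The cost is a manual check of the form version for SGRQs completed after approval, plus a version flag in the analysis data; Protocol Tables 1 and 2 list no such field. The check is feasible: E1 is already a manual check, and the protocol abstract (Data sources) has completed questionnaires kept at the centres for data review. It is best settled before the analysis, since 6.6 also bars correcting implausible values patient by patient and so leaves little room for an unplanned repair. If the unseen text already blanks question 17 by form version, one clarifying sentence in 6.6 and 7.4.1 is enough.
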